4.1.6 PI assessment and reporting

The laboratory results, clinical assessment, x-rays and MRI reports will be sent to the local PI. The local PI (or delegate) will then review all clinical and diagnostic parameters. Diagnostic confidence will be reported on an 8 point Likert scale as described in Table 2 (Section 3.2), with scores of 7 or 8 considered as diagnosed with axSpA. Reviewing rheumatologists will not be provided with any results from existing screening tools to inform the presence or absence of axSpA. The ASAS axSpA classification [1] (see 3.1.2 Reference standard) will be a secondary reference standard.

The participant will be informed by the local PI (or delegate) whether or not they are likely to have axSpA or whether their back pain is likely to be due to non-inflammatory causes. A summary of the laboratory, x-ray and MRI reports will be forwarded to the participant's GP. The participant will also receive publicly available advice leaflets/website links, related to their diagnosis from the research site team.

If axSpA diagnosis is unclear, then it will be flagged to the GP in this letter. For patients with an equivocal likelihood of axSpA, further clinical investigation might be required in the future time in either primary or secondary care (at the discretion of the patient's primary care team).

All reports will be entered to the study database by site clinicians, or their delegates. This will include any diagnostics of serious conditions.

4.2 Study Procedures

4.2.1 Blood sampling

Blood will be collected and processed as per local hospital laboratory standard operating procedures. The blood samples will be tested for the presence of HLA-B27 and CRP level. The samples will then be destroyed.

Where additional, and optional consent has been provided, additional blood samples will be collected and stored for biomarker analysis, which will be covered by separate ethics and HRA approval.

4.2.2 Imaging

Radiographs

For participants aged 18 and over, conventional SIJ plain x-rays will be taken.

Page 32 of 53

IDEAL BACKPACS Protocol Final Version 1.1 date 09-Oct-2024

MRI

MRI scans will be acquired according to a dedicated imaging protocol. Participants will have an MRI scan of their SIJ and whole spine (30 min scan) arranged within 4 weeks (where possible) of clinical assessment. For some secondary care sites, the MRI scan may be on the same day as the clinical assessment, if there is capacity. MRI scans will be acquired according to a dedicated imaging protocol which will be provided separately.

Briefly, SIJ MRI acquisitions will be performed in modified coronal plane (aligned with the long axis of the SIJ), using small field-of-view imaging and consistent resolution (matrix size) between the acquisitions.

We will acquire:

- T2-weighted STIR or turbo STIR imaging
- T1-weighted turbo spin echo imaging a
- T2-weighted Dixon turbo spin echo imaging (repeated with two effective echo times).

For the spine imaging, we will cover the whole spine in the sagittal plane, using either two or three blocks, using (i) T2-weighted STIR or 'turbo' STIR imaging and (ii) T1-weighted turbo spin echo imaging.

Data upload

Image data will be acquired in DICOM format and pseudo-anonymised by individual sites, before being uploaded to the XNAT platform for image storage and curation. Each site will have their own folder on the XNAT platform to minimise the risk of data leaks between sites.

Scan interpretation

All scans will be read by two consultant radiologists on the XNAT platform. If discrepancies exist regarding the overall impression of whether axSpA is present (i.e. whether the patient is 'imaging positive') across the MRI and x-ray, a third consultant radiologist will perform an additional read and make a final decision on the appropriate category.

The following will be included in the x-ray report:

Modified New York criteria grade 0-4 for each SIJ.

The following will be included in the MRI report:

- Description of oedema and structural features (fat metaplasia, erosions, ankylosis) in SIJs – yes/no for each.
- Interpretation according to ASAS specifications (bone marrow oedema in typical location 'highly suggestive' of axSpA) - yes/no for MRI positivity
- Are there unequivocal features of spinal inflammation? yes/no

The following will be included as an overall interpretation across MRI and x-ray: (a) normal (b) equivocal (c) axSpA (d) other

ASAS specifications (bone marrow oedema and structural changes)

4.2.3 Post Study Care

Once the participant has completed all study assessments they will receive a letter with their diagnosis and publicly available advice leaflets/website links from the local PI (or delegate).

Page 33 of 53
IDEAL BACKPACS Protocol Final Version 1.1 date 09-Oct-2024

TIDEAE BAONI AGGI TOLOGGI FINAL VCISION 1.1 GALG 03-GGE-202-

Participants identified as having axSpA will be followed up (outside of this research study) in standard NHS Rheumatology outpatient clinics.

Participants without axSpA will be provided with self-management advice and could seek further support from their GP.

In addition to a clinical research evaluation of each participant's MRI scan (which might occur some weeks after performed), a local standard NHS report of each MRI will be performed, by the radiology team where the MRI scan has taken place, and sent to the local PI at each research site. These reports will be available in the same time frame as a standard NHS non-research MRI report. These local reports will act as a safety measure, so that in the rare instance of an unexpected serious (non-inflammatory) pathology, such as malignancy, vertebral collapse or infection, causing the participant's symptoms, this pathology would be identified. The local PI would then communicate these findings to the participant's GP to ensure appropriate intervention and treatment occurs.

4.2.4 Compliance

The study analysis requires 720 participants with a complete screening dataset. We aim to recruit a total of up to 900 participants to allow for up 20% of participants not completing all study procedures. Compliance with study procedures will be monitored via data entered into the study database. Only those with a complete screening dataset will be included in the analysis.

4.2.5 Criteria for terminating study

There are no set criteria for terminating the study and an interim analysis is not planned. The study will be monitored by the programme management group and programme steering committee, who will receive regular progress updates. The PMG and PSC will only consider termination of the study if major insurmountable issues are identified.

4.5. Radiation exposure

4.5.1 Details of diagnostic or therapeutic ionising radiation

For participants aged 18 and over, conventional SIJ plain x-rays will be taken.

Procedure	No of procedures	Estimated procedure dose
x-ray of pelvis/SIJ	1	4mGy/2.2 Gy/Cm2

4.5.2 Clinical Assessment

We estimate that 70% of participants would eventually be investigated for axSpA therefore additional ionising radiation exposure relates to 30% of our cohort. The exposure will not exceed the exposure that might be received as part of normal care at any proposed research site.

Page 34 of 53
IDEAL BACKPACS Protocol Final Version 1.1 date 09-Oct-2024

4.6 Collection, Storage and Analysis of Clinical Blood Samples (HLA-B27 / CRP)

The blood samples will be tested for the presence of HLA-B27 and CRP level. Collection, storage and analysis of clinical blood samples will be in line with local secondary care laboratories standard operating procedures. Samples for NHS pathology analysis will be labelled in accordance with local NHS procedures. Samples will not be retained at the end of the study and will be destroyed in accordance with the Human Tissue Act, 2004.

It is the responsibility of the study site to ensure that samples are appropriately labelled in accordance with the study procedures to comply with the 2018 Data Protection Act. Biological samples collected from participants as part of this study will be transported, stored, accessed and processed in accordance with national legislation relating to the use and storage of human tissue for research purposes and such activities shall at least meet the requirements as set out in the 2004 Human Tissue Act and the 2006 Human Tissue (Scotland) Act.

5. STATISTICS

5.1 Methods

The analysis and reporting of the study will be in accordance with STAndards for Reporting of Diagnostic Accuracy (STARD) and Transparent Reporting of a multivariable prediction model for Individual Prognosis Or Diagnosis + Artificial Intelligence (TRIPOD+AI) reporting guidelines. A full statistical analysis plan (SAP) will be developed and agreed prior to database lock.

Descriptive statistics will be used to describe baseline characteristics, prevalence of axSpA symptom duration, pain severity and other clinical factors.

For each of the index tests (described in section 3.3) sensitivity, specificity, positive and negative predictive values, and likelihood ratios (and associated 95% confidence intervals) will be calculated to assess diagnostic accuracy and clinical utility, along with the area under the (receiver-operator characteristic) curve and calibration. Estimates of comparative accuracy between models will be obtained using appropriate statistical models and reported with 95% confidence intervals. Where necessary we will recalibrate models to allow for a difference in prevalence of disease in our population.

To develop the BACKPACS strategy we will pre-specify 12 key variables to include in the initial modelling, although we would seek to develop models with 3 or 4 variables which would be most suitable for clinical use. Internal validation using 200 bootstrap samples and shrinkage will correct for overfitting. A prediction model equation or simplified clinical score will be presented in a user-friendly format, with performance summarised using discrimination (c-index) and calibration (plot in quartile risk groups) outcomes and graphs. Based on estimates of sensitivity and specificity, we will determine a sensible cut-off value above which patients could be referred to a rheumatologist.

Analyses will be conducted in Stata 18.0 or later.

Planned Subgroup Analyses

Where feasible, subgroup analyses will be employed to assess whether there are differences in accuracy of the referral strategies for the following groups:

Page 35 of 53 IDEAL BACKPACS Protocol Final Version 1.1 date 09-Oct-2024

- Age of symptomatic onset before 35 years vs. onset after 35 years
- Males/Females
- Caucasian vs non-Caucasian (related to variations in disease incidence with race)

Subgroup analyses will be conducted by including an appropriate interaction term in the statistical model.

5.2 Sample size and justification

The prevalence of axSpA is predicted to be similar to the 14.1% prevalence reported in the Baraliakos study [9] Assuming a 14% axSpA prevalence, and a Baraliakos referral strategy with sensitivity 90% and specificity 65%, a total of 720 patients will provide over 90% power to detect lower bounds of sensitivity 79% and specificity 58% allowing for 20% participants without full data (either due to non-attendance at clinic visits or uncertainty in estimates of prevalence/test accuracy). Once 720 participants complete follow up and are fully assessable for clinical diagnosis of axSpA, recruitment will cease. This is due to the high costs of additional clinical review/MRI scans.

This sample size is sufficiently powered for the development of a model based on 12 variables with 0.8 c-index and allowing for 10% shrinkage to correct for overfitting.

5.3 Procedures for missing, unused and spurious data

The primary analysis will include participants who have provided complete data (i.e. for whom the index test and reference standard can be determined). The sensitivity of the findings to different assumptions about missing data will be explored through sensitivity analyses, which will be fully specified in the Statistical Analysis Plan (SAP).

5.4 Definition of populations analysed

The primary analysis will be conducted for participants who have provided complete data. Sensitivity analyses (fully specified in the SAP) will include all participants..

6. HEALTH ECONOMICS

Aim

The objective of the health economics analysis is to assess the cost-effectiveness of different axSpA referral strategies, comparing strategies with current care and a comparison between strategies in a fully incremental analysis, applying the rules of simple and extended dominance. A cost-utility analysis will be undertaken to calculate cost per quality-adjusted life year (QALY) gained from an NHS perspective. NICE thresholds of £20,000/QALY and £30,000/QALY will be applied to the results.

Outcome measurement

The cost-effectiveness analysis will use pre-existing equations, as developed and advised by NICE 2017 clinical guideline for spondyloarthritis. This is specified in the section outlining the analysis approach. Outcome data required for the equations for each referral strategy will be available from WP2, namely the prevalence of the condition and test sensitivity and specificity. Data on quality of life is not required as this has already been factored into the model equations using utilities for health states.

Page 36 of 53
IDEAL BACKPACS Protocol Final Version 1.1 date 09-Oct-2024

Resource Use Measurement

Data on the health care resource use required for each referral strategy will be collected during WP2 (e.g., tests administered, or extra appointments required) costs calculated using standard NHS unit costs.

Analysis

As part of the development of latest NICE clinical guidelines in axSpA, a detailed model-based economic evaluation of axSpA referral strategies was constructed [3]. The Markov model, with a 3-month time cycle and lifetime time horizon estimated the costs and utility of being correctly identified with axSpA and being misdiagnosed and therefore being treated for chronic low back pain of unknown cause. The evaluation of a superior referral strategy included a complex interaction of the benefits, costs and harms associated with false-positive and false-negative diagnoses, with potential approaches trading off sensitivity and specificity. A key output of the model is two equations, one for discounted costs and one for discounted QALYs to allow assessment of the cost-effectiveness of future referral strategies, without researchers having to reconstruct the decision model. We therefore propose to use these equations in our analysis.

The equations are:

Costs = $\mathbf{C} + \mathbf{v} \mathbf{n} 107,307 + \mathbf{v} (1-\mathbf{n}) 104,966 + (1-\mathbf{v}) (1-\mathbf{p}) 559$

QALYs= vn14.571 + v(1-n)13.534

Where C is the initial cost of the strategy, v is the true prevalence of axSpA among people with chronic back pain of ≥ 3 months' duration with age of onset ≤ 45 , n is the sensitivity of the strategy and p is the specificity of the strategy.

The equation for the incremental cost-effectiveness ratio (ICER) versus current care (as specified in the NICE guidelines) is as follows:

ICER=
$$\underline{C} + vn107,307 + v(1-n)104,966 + (1-v)(1-p)559-5,264$$

 $vn14.571 + v(1-n)13.534-0.682$

The strategies for comparison will be the validated Baraliakos strategy, the alternative UK referral strategy (BACKPACS) and existing referral strategies assessed by the original NICE model.

Health economic uncertainty will be explored by changing the values of the equation variables to assess the robustness of the results. Due to the nature of the analysis with predetermined equations, probabilistic sensitivity analysis will not be undertaken, therefore Cost Effectiveness Acceptability Curves (CEACs) will not be presented.

Model development

The health economic model results will be used as part of the iterative process to design the 'superior' BACKPACS referral strategy. The initial estimates for Baraliakos and BACKPACS referral strategies will be entered into the equations and cost-effectiveness estimated. The effectiveness (specificity/sensitivity/likelihood ratio), cost-effectiveness estimates and feasibility (ease of implementation) will all be part of the package of information on the strategies provided to the CoP and PPI groups for discussion. Factors included in feasibility considerations would include variables that might be completed at a single GPC consultation (i.e., presence of buttock pain, previous history of enthesitis or uveitis), versus factors that would require further evaluation or clinic attendance (i.e., response to NSAIDs or blood test results (CRP / HLA-B27). Any changes to the BACKPACS strategy will then be factored into Page 37 of 53

IDEAL BACKPACS Protocol Final Version 1.1 date 09-Oct-2024

the analysis and results re-estimated. A number of cycles of statistical and health economic modelling and then CoP/PPI consideration may be required, before an eventual 'superior' referral strategy is determined.

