4.1 Schedule of assessments

4.1.1 Invitation and screening

Initial eligibility to approach is confirmed by the GPC during the primary care attendance. Patients aged 16-50 years who present with chronic back pain (with onset before 45 years) and do not present with any suspected red flags (as described in section 3.4.2 Eligibility criteria) will be approached. Basic screening information obtained from the consultation will be recorded on the pop-up.

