7. ADVERSE EVENTS

Reporting Requirements

The occurrence of an adverse event as a result of participation within this study is not expected and no adverse event data will be collected.

The risks of participating in this study are comparable to that of usual care. The clinical assessments are conceptually similar to what might have been done as part of usual practice. For example, participants may already be sent questionnaires about their condition and history before further clinical investigations take place. The clinical investigations in the study are all completed as per the NICE 2017 clinical guidelines for spondyloarthritis.

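### The ICER subtracts a fixed current-care total that fits a prevalence near 5%, not the expected 14%, and the cohort records no usual-care referral decision from which to rebuild it

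*Protocol*

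**What the plan says.** Section 6 (and the last objective in 2.3) sets current care as a comparator: "comparing strategies with current care and a comparison between strategies in a fully incremental analysis". The list of options reads: "The strategies for comparison will be the validated Baraliakos strategy, the alternative UK referral strategy (BACKPACS) and existing referral strategies assessed by the original NICE" (meaning the guideline's economic evaluation). This study supplies prevalence, sensitivity, specificity and resource use for each referral strategy; current care is not among them.

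The QALY equation is "QALYs= vn14.571 + v(1-n)13.534", where v is the prevalence, n the sensitivity and p the specificity. The ICER numerator is C plus "vn107,307 + v(1-n)104,966 + (1-v)(1-p)559-5,264" and the denominator is "vn14.571 + v(1-n)13.534-0.682". Current care is thus £5,264 and 0.682 QALYs, attributed to the NICE guideline. Uncertainty is to be explored by changing the equation variables; probabilistic analysis is ruled out.

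On data capture, 4.1.1 says "Basic screening information obtained from the consultation will be recorded on the pop-up". Section 3.4.1 describes that content as current pain, duration, red flags and agreement to a text message. The eligibility call and Tables 4 to 6 list no usual-care referral decision.

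Section 4.5.2 gives a separate picture of what would happen without the study: "We estimate that 70% of participants would eventually be investigated for axSpA therefore additional ionising radiation exposure relates to 30% of our cohort".

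**The concern.** Every term of the QALY equation is multiplied by v, because only people with axSpA contribute QALYs. A strategy's total therefore rises in proportion to the prevalence entered. The comparator is a fixed number that does not move. Unless v happens to equal the prevalence behind 0.682, the subtraction mixes the effect of the referral strategy with a difference in how many people have the disease.

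The study will enter its own v, and section 5.2 expects 14%. The comparison with current care, a stated objective, could then consist mostly of this mismatch. The planned sensitivity analysis would not show it, since varying v moves the strategies and leaves the comparator where it is.

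The cohort could supply a proper comparator. Every participant receives the reference work-up, so the usual-care referral decision could be scored like any index test. As listed, it is not collected.

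**Working it through.** **Inputs.** Equations and constants from section 6; v = 0.14, n = 0.90, p = 0.65 from section 5.2. C is not given, so results are before C. In the common-prevalence comparisons, C means the strategy's initial cost net of current care's.

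**1. The printed ICER at the protocol's inputs.**
- Cost = 0.14×0.90×107,307 + 0.14×0.10×104,966 + 0.86×0.35×559 = 13,520.7 + 1,469.5 + 168.3 = £15,158.
- QALYs = 0.126×14.571 + 0.014×13.534 = 2.025.
- Increments: 15,158 − 5,264 = +£9,894; 2.025 − 0.682 = 1.343 QALYs. ICER about £7,365.

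**2. Can the constants arise at 14%?**
- QALYs run from 0.14×13.534 = 1.895 (n = 0) to 0.14×14.571 = 2.040 (n = 1).
- Cost runs from 0.14×104,966 = £14,695 (n = 0, p = 1) to 0.14×107,307 + 0.86×559 = £15,504 (n = 1, p = 0).
- Neither £5,264 nor 0.682 is reachable. The largest possible gain over any comparator is 0.14×(14.571 − 13.534) = 0.145 QALY. The printed 1.343 is about nine times that.

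**3. Which prevalence fits 0.682?** Between 0.682/14.571 = 0.0468 and 0.682/13.534 = 0.0504. This does not depend on C.

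**4. What accuracy do the constants imply?** Solving both equations with C = 0:

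| v (assumed) | n | 1 − p | share referred = vn + (1−v)(1−p) |
|---|---|---|---|
| 0.047 | 0.942 | 0.426 | 0.044 + 0.406 = 45% |
| 0.050 | 0.102 | 0.007 | 0.005 + 0.007 = 1% |

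The constants do not identify what current care does; the answer turns on the third decimal of v.

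**5. How much of the printed increment is mismatch?** Take current care as n = 0.102, 1 − p = 0.007 (the v = 0.05 solution) and run it at v = 0.14. Baraliakos then gains 0.116 QALY at +£426. So 9,894 − 426 = about £9,470, and 1.343 − 0.116 = about 1.23 QALYs, come from the unequal prevalences. As a check, the printed formula at v = 0.05 gives +£275 and 0.041 QALY; scaling by 0.14/0.05 = 2.8 gives about 0.116, not 1.343.

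**6. Current care at the same v = 0.14, with assumed accuracies.** No document gives these. With Baraliakos at 90%/65%, incremental cost = 0.14×(0.90 − n)×2,341 + 0.86×(p − 0.65)×559, where 2,341 = 107,307 − 104,966. Incremental QALYs = 0.14×(0.90 − n)×1.037.

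| Current care, sensitivity/specificity | QALYs | Cost before C |
|---|---|---|
| 10%/98% | +0.116 | +£421 |
| 30%/90% | +0.087 | +£317 |
| 50%/80% | +0.058 | +£203 |
| 70%/30% | +0.029 | −£103 |

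**7. Headroom for C at £20,000 per QALY.**
- Printed formula: 20,000×1.3434 − 9,894 = about £16,974 per person.
- Common v, 10%/98%: 20,000×0.11614 − 421 = about £1,902.
- Common v, 70%/30%: 20,000×0.02904 + 103 = about £683.

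**The case against.** **Published constants were a deliberate choice.** The protocol adopts existing equations so that the decision model need not be rebuilt, and not collecting referral decisions is no error in itself. That stands. Comparisons between strategies are also untouched, because the constants cancel. The choice does not, however, justify subtracting a comparator at one prevalence from a strategy at another.

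**The conclusion may not change.** Before C, the positive rows in step 6 give about £3,500 to £3,640 per QALY, the last row is cheaper and more effective, and the printed formula gives about £7,365. All are below £20,000. That stands before C, but step 7 shows that the printed formula makes the result almost insensitive to C.

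**A referral question is an imperfect measure.** It covers one consultation, is prompted by the study, and may be displaced by the invitation. Patients found by retrospective search have no index consultation to ask about. This stands and calls for sensitivity analysis.

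**Stronger readings the documents do not support.**
- A reader might infer that the sign of the incremental cost is undetermined. Under the printed formula it is fixed: +£9,894 plus C. A negative value needs current care restated at 14%, the 70% of 4.5.2 read as an uninformative referral rate, and a net initial cost below about £103.
- A reader might set the 70% against the 0.14×0.90 + 0.86×0.35 = 42.7% that Baraliakos would refer, and conclude that at least 57% would have extra X-rays. But 70% is an eventual figure with no time frame, whereas 42.7% is one application of one rule. Rule-negative patients may be investigated later, so 57% has no basis.
- The remark in 1.1 that guidelines make no axSpA-specific referral recommendation concerns general back-pain guidance; 1.2 notes that NICE suggested the modified Braun strategy.
- Section 7's statement that "The risks of participating in this study are comparable to that of usual care" rests on the type of assessment and on NICE guidance, not on the 70%.

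**Conclusion.** The concern holds for the comparison with current care. At 14% prevalence the printed ICER subtracts a comparator that the protocol's own equations cannot produce. It reports a gain of 1.343 QALYs where at most 0.145 is possible, and most of the +£9,894 has the same cause. This rests on current care following the same QALY equation as the strategies, and on v being the study's own estimate near 14%. The source guideline is not at hand, so the prevalence of about 4.7% to 5.0% is what the protocol's equations require, not a figure it states.

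On a common prevalence, the gain over current care varies fourfold (0.116 to 0.029 QALY) across the assumed accuracies. Nothing in the listed data collection would narrow that range. The 70% in 4.5.2 is not shown to be wrong. Its basis is unstated, and it is not linked to the comparator in section 6.

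**What to change.** 1. **Common prevalence.** In section 6, replace the two constants with current care computed from the same cost and QALY equations at the same v as the strategies, with its own n, p and initial cost. The published constants can stay as a secondary analysis at a prevalence they fit. This costs only a change of text.

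2. **One data item.** Add a yes/no item to the pop-up or eligibility-call form: was a rheumatology referral made, or would one have been made without the study? Analyse it as a further index test against the primary reference standard. With 720×0.14 = about 101 cases, a sensitivity of 30% (assumed) would have a 95% half-width of about 1.96×√(0.3×0.7/101) = 9 percentage points, enough to separate the first three rows in step 6. The cost is one form item and one more row in the accuracy and cost-effectiveness tables.

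3. **Sensitivity analysis.** Vary current-care sensitivity and specificity over a stated range, because the answer is partly hypothetical. For retrospective-search recruits it must come from the record or the participant; report them separately.

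4. **Section 4.5.2.** State the basis and time frame of the 70%/30% estimate and reconcile it with the current-care comparator in section 6. No replacement figure is proposed.

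### The ICER against current care holds the comparator at about 5% axSpA prevalence while the strategy is evaluated at the study's own prevalence, expected to be 14%

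*Protocol*

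**What the plan says.** Section 6 (Analysis) takes over two equations from the NICE guideline model. The QALY equation is "QALYs= vn14.571 + v(1-n)13.534". The cost equation adds an initial strategy cost C, terms for detected and missed axSpA that are proportional to v, and £559 per false positive. The same section defines the variables: "v is the true prevalence of axSpA among people with chronic back pain", n is sensitivity and p is specificity.

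The ICER against current care, attributed to the guideline, then subtracts two fixed numbers. Apart from C, its numerator is "vn107,307 + v(1-n)104,966 + (1-v)(1-p)559-5,264" and its denominator is "vn14.571 + v(1-n)13.534-0.682". Neither constant contains v. The protocol does not say at what prevalence they were obtained, and it does not tell the analyst to recompute them.

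Section 6 (Outcome measurement) says the inputs will come from this study, "namely the prevalence of the condition and test sensitivity and specificity". Section 5.2 plans on "Assuming a 14% axSpA prevalence". The results are to be read against £20,000 and £30,000 per QALY, and comparison with current care is part of a secondary objective in Section 2.3.

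**The concern.** The QALY equation counts only people with axSpA; everyone else contributes zero. Total QALYs, and nearly all of the cost, therefore rise in proportion to v, whatever the referral rule does. An increment is meaningful only if both sides use the same v. If current care stays at a low prevalence and the strategy is evaluated at a higher one, the difference mostly counts the additional axSpA patients and not the effect of the strategy.

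At stake is the comparison with current care and its reading against the two thresholds. Cost-effectiveness estimates are also one of the inputs given to the advisory groups when the BACKPACS strategy is refined.

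**Working it through.** **Inputs.** From Section 6: 14.571 and 13.534 QALYs and £107,307 and £104,966 per detected and missed case; £559 per false positive; current care £5,264 and 0.682 QALYs. From Section 5.2: v = 0.14, sensitivity 0.90, specificity 0.65. The documents give no value for C and no accuracy for current care (n0, p0, C0).

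**1. What prevalence do the constants imply?**
- QALYs = v × (13.534 + 1.037n), with n between 0 and 1. So 0.682 needs v between 0.682/14.571 = 4.68% and 0.682/13.534 = 5.04%.
- The lowest possible cost is v × 104,966. So £5,264 needs v of at most 5,264/104,966 = 5.01%.
- The two constants reproduce together at v = 5% with C0 = 0. From the QALYs, n0 = (0.682/0.05 − 13.534)/1.037 = 0.102. Cost before false positives is then 0.05 × (104,966 + 2,341 × 0.102) = £5,260. The remaining £3.7 equals 0.95 × 559 × (1 − p0), giving p0 = 0.993.

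**2. Can they hold at 14%?** No. The minimum over all sensitivities and specificities is 0.14 × 104,966 = £14,695 and 0.14 × 13.534 = 1.895 QALYs.

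**3. A strategy that refers nobody (n = 0, p = 1, C = 0), printed formula.**
- At v = 14%: (14,695 − 5,264)/(1.8948 − 0.682) = 9,431/1.2128 = £7,777 per QALY.
- At v = 8%, 10% and 20%: £7,819, £7,794 and £7,768.
- At v = 5%: −£15.7 and −0.0053 QALYs, a small loss, as it should be.

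This check needs no assumption about current care.

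**4. Sensitivity 0.90, specificity 0.65, v = 14%, printed formula.** Cost is £15,158 + C and QALYs are 2.0254. The increments are £9,894 + C and 1.343 QALYs, so £7,365 per QALY at C = 0.

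**5. QALY gain with a matched comparator.** The gain is 0.14 × (0.90 − n0) × 1.037. Its largest value, at n0 = 0, is 0.131. The overstatement is at least 1.343/0.131 = 10.3-fold.

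**6. Effect on the ICER (assumed n0 = 0.102, p0 = 0.993, C0 = 0).** Current care at 14% costs £14,732 and gives 1.910 QALYs, so the matched increments are £426 + C and 0.1158 QALYs.

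| Assumed C | Printed ICER | Matched ICER |
|---|---|---|
| £0 | £7,365 | £3,681 |
| £500 | £7,737 | £7,998 |
| £1,000 | £8,109 | £12,315 |
| £2,000 | £8,854 | £20,949 |
| £5,000 | £11,087 | £46,851 |

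- The two ICERs cross at C of about £467.
- The matched ICER reaches £20,000 at C = 20,000 × 0.1158 − 426 = about £1,890. The printed one reaches it at C = 20,000 × 1.3434 − 9,894 = about £16,970.

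**7. How far step 6 depends on the assumption.** Two constants do not identify v, n0, p0 and C0. A basis of v = 4.8% fits equally well with n0 = 0.65 and p0 = 0.71. The matched increments at 14% are then about £112 + C and 0.0363 QALYs. The crossing moves to about £159, and the matched ICER reaches £20,000 at 20,000 × 0.0363 − 112 = about £613. Steps 1 to 5 do not change.

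**The case against.** **The formula is the guideline's own.** That gives its source, but it does not make it valid at another prevalence: Section 6 defines v as a variable and supplies it from this study.

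**Sensitivity analysis will cover it.** Section 6 varies the equation variables. The two constants are not among them, so varying v repeats the mismatch, as step 3 shows.

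**The size and direction for real strategies rest on unknown costs.** This stands. The documents give no C, and at low C no threshold verdict changes. A reader might infer that every strategy lands at about £7,000 to £10,000 per QALY and passes. The arithmetic does not support that: at 0.90/0.65 the printed ICER exceeds £10,000 once C is above about £3,540 and £20,000 once C is above about £16,970. Nor does the formula always flatter a strategy; for a cheap one the printed ICER is too high.

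**The choice between Baraliakos and BACKPACS is not contaminated.** This also stands. In an incremental comparison of two strategies at a common v the constants cancel, and cost-effectiveness is only one input beside accuracy and feasibility.

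**No probabilistic analysis.** A reader might take the statement that "probabilistic sensitivity analysis will not be undertaken" as part of the same error. It is not. It is a declared choice with a stated reason and a deterministic alternative, and it contradicts nothing in the protocol.

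**Conclusion.** The ICER against current care is wrong as printed whenever the study's prevalence is not close to 5%. Three results rest on the protocol's figures alone: the constants imply a prevalence of about 4.7% to 5.0%; at 14% no accuracy values can produce them; and a strategy that refers nobody appears to gain 1.21 QALYs at about £7,777 per QALY. The QALY gain of a 0.90/0.65 strategy is overstated at least 10-fold.

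The consequence for the ICER is conditional. With back-solved n0 of about 0.10 and p0 of about 0.993, it is too high for C below about £470 and too low above that. A £20,000 verdict is reversed only for C between about £1,900 and £17,000. Other comparator values that fit the constants would move the crossing and the lower limit.

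The 14% is a planning assumption, and the distortion follows whatever prevalence is observed. Below 5% it reverses: at v = 3% the same strategy would appear to lose 0.248 QALYs. The defect is confined to the comparison with current care. The co-primary objectives, the sample size and the accuracy analyses are untouched.

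**What to change.** In Section 6, replace £5,264 and 0.682 with current care evaluated at the same v as the strategies:

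- cost_cc = C0 + v × n0 × 107,307 + v × (1 − n0) × 104,966 + (1 − v) × (1 − p0) × 559
- QALY_cc = v × n0 × 14.571 + v × (1 − n0) × 13.534

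Take current care's sensitivity n0, specificity p0 and initial cost C0 from the guideline model and state them in the protocol. The back-solved values above are a check, not a source. Use this comparator in the fully incremental analysis as well, and recompute it whenever v is varied in sensitivity analysis. As a test, entering n0, p0 and C0 as a strategy should return zero increments at any v, and at the guideline's prevalence cost_cc and QALY_cc should return £5,264 and 0.682.

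The cost is a change of wording and a few lines of code before analysis. No data collection, sample size or accuracy analysis changes.
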